11.2. Reporting of Adverse Events

All Adverse Events (except unavoidable events listed in Section 11.3), regardless of relatedness or outcome, must be reported. The investigator is responsible for reporting all AEs to Medtronic and for their follow up.

Pain, neurological, and function symptoms should be reported as an adverse event when a subject's

Medtronic Controlled Information

complaint for any of these symptoms results in an unscheduled visit or when a subject presents with clinically significant new or worsening pain, neurological and/or function symptoms as compared to the previous visit.

All adverse events will be classified using the following responsibility matrix:

Table 8. Adverse Event Classification Responsibilities

What is classified?	Who classifies?	Classification Parameters
Relatedness	Investigator	Device, Procedure
	Sponsor	Device, Procedure
Seriousness	Investigator	SAE, DD with SADE potential
	Sponsor	SAE, DD with SADE potential
Severity	Investigator	Mild, Moderate, Severe, Life Threatening
Diagnosis	Investigator	Based on presenting signs and symptoms and other supporting data
	Sponsor	MedDRA term assigned based on the data provided by Investigator
Expectedness	Sponsor	UADE/USADE

From the time that the assent/informed consent forms are signed, all reportable events must be recorded in the subject’s medical record and on the Adverse Event and/or Device Deficiency eCRF and promptly reported to Medtronic. IRB/EC/REB reporting must be completed in accordance with the policies of the governing IRB/EC/REB. Regulatory Authority reporting should be in accordance with applicable local regulations.

It is the responsibility of the investigator to identify the occurrence of adverse events and device deficiencies and to ensure the required information is accurately documented on the eCRF.

Reports of adverse events and device deficiencies will include the following information, at a minimum:

- Date of event
- Date site became aware of the event
- Diagnosis or description of the event
- Assessment of the seriousness and relationship to the device and/or surgical procedure
- Treatment provided

- Outcome and date of resolution

The clinical course of each adverse event must be followed until resolution, subject discontinuation from the study or last study follow up visit, whichever comes first. “Not resolved” adverse events and device deficiencies must be assessed at each protocol required visit, and new or updated information must be documented on the Adverse Event and/or Device Deficiency eCRF and promptly reported to Medtronic and where applicable to the IRB/EC/REB. At time of study exit, the status of all unresolved Adverse Events should be evaluated and should reflect the subject's status at time of study exit.

Upon request of Medtronic, de-identified source documentation should be provided to Medtronic. When printouts of original electronic source documents are obtained, these shall be signed and dated by a member of the investigator site team with a statement that this is a true reproduction of the original source document.

Upon request of Medtronic, de-identified images should be provided to Medtronic.

Medtronic study personnel will promptly review all reported adverse events and device deficiencies and if necessary, request clarification and/or additional information from the investigator. If Medtronic disagrees with the Investigator's assessment of the adverse event seriousness and relationship to the device and/or procedure, Medtronic study personnel will document the disagreement and report or ensure reporting of both opinions to the IRB/EC and regulatory authority as necessary. In addition, aggregate safety data will be reviewed and analyzed to identify potential safety issues, signals, and trends at minimum, annually.

Investigators must report applicable events and product deficiencies to Medtronic and where appropriate, to an IRB/EC/REB or regulatory authority. Details (e.g., date of event, treatment, resolution, seriousness, relationship to the product) of the events and product deficiencies must be documented in the medical record and reported to Medtronic per Table 10.

11.3. Not reportable events

Examples of events that are not reportable as adverse events for this study are:

- A documented pre-existing condition unless there is a worsening of the nature, severity, duration, or frequency of that condition.
- Elective or Preventative medical procedures (e.g., tooth extraction, cosmetic surgery); however, the condition leading to the procedures might be a reportable event if there is a worsening of the nature, severity, duration, or frequency of that condition.

Table 9 provides a list of Unavoidable Adverse Events (UAE). An UAE will not be considered reportable unless it worsens or is present outside the stated timeframe post-procedure.

[figure not shown]

Table 9. Unavoidable Adverse Events (UAEs)

Event Description	Timeframe from the Surgical Procedure
Anesthesia related nausea / vomiting	24 hours
Low-grade fever (<100°F or 37.8°C)	48 hours
Mild to moderate bruising / ecchymosis	7 days
Seroma	72 hours
Sleep problems (insomnia)	72 hours
Back pain related to laying on the table	72 hours
Shoulder pain/discomfort/stiffness	72 hours
Pneumothorax, non-serious	72 hours
Supplemental Oxygen with no other	24 hours
Blood loss less than 800 cc	24 hours

11.4. Device Deficiencies

A device deficiency (DD) is an inadequacy of a medical device with respect to its identity, quality, durability, reliability, safety or performance. Device deficiencies include malfunctions, use errors, and inadequate labeling. All device deficiencies must be documented and submitted to Medtronic on the Device Deficiency eCRF. In addition, the investigator must also determine and document on the eCRF device deficiencies that did not lead to adverse event but could have led to a serious adverse device effect:

- If either suitable action had not been taken,
- If intervention had not been made, or
- If circumstances had been less fortunate
- Refer to Table 10 for investigator reporting timelines for device deficiencies.

11.5. Reporting Adverse Events to Medtronic

Investigator reporting timelines can be found in Table 10. The preferred way of transmission of AEs and DDs is the RDC system, but in case the eCRF cannot be accessed, the investigator should contact study personnel by e-mail to report. The AE/DD worksheet provided to investigators may be used for completion of available information, preferably signed by investigators and attached to the email. The same CIP reporting timelines apply for all types of reporting as if the eCRF would be available.

Table 10. Required timeframes for Adverse Advent Reporting by Investigator

Required Timeframes for Adverse Event reporting from Investigator to Medtronic	
Event Type	Timeframe for Reporting
Serious Adverse Event (SAE)	Immediately (but no later than 3 calendar days) after the investigator first learns of the event or of new information in relation with an already reported event.
Serious Adverse Device Effect (SADE)	
Unanticipated Adverse Device Effect (UADE)	
Unanticipated Serious Adverse Device Effect (USADE)	
Device Deficiencies with SADE potential	
All Other Adverse Event (AE)	In a timely manner after the investigator first learns of the event
All other Device Deficiencies	
Required Timeframe for Adverse Event reporting from Investigator to Health Canada (for Canadian sites only)	
Serious Adverse Device Effect (SADE)	In Canada, SADEs on the subject, the user or any other person must be reported to Health Canada and to the sponsor within 72 hours after it comes to the attention of the qualified investigator.
Unanticipated Adverse Device Effect (UADE)	In Canada, UADEs on the subject, the user or any other person must be reported to Health Canada and to the sponsor within 72 hours after it comes to the attention of the qualified investigator.
Unanticipated Serious Adverse Device Effect (USADE)	In Canada, USADEs on the subject, the user or any other person must be reported to Health Canada and to the sponsor within 72 hours after it comes to the attention of the qualified investigator.
Device Deficiencies with SADE potential	In Canada, DDs that have resulted in any of the consequences characteristic of an SAE on the subject, the user or any other person or could do so were it to reoccur must be reported to the regulator and the Sponsor within 72 hours after it comes to the attention of the qualified investigator.

The AE reporting period for each subject starts when the subject and/or parent/legal guardian signs the Informed Consent/Assent and continues at all subsequent visits through the end-of-study. Any pre-existing conditions that are detected as part of the screening procedures should be reported on the

Medtronic Controlled Information

prior medical history form and not as AEs. However, pre-existing conditions that worsen during the study will need to be reported as AEs.

If possible, a specific diagnosis should be recorded, rather than a listing of individual signs and symptoms. In addition, investigators are obligated to report adverse events in accordance with the requirements of their reviewing IRB/EC/REB and regulatory authority (where applicable). The Sponsor is obligated to report AEs that occur during this trial to the Regulatory Authorities and IRB in compliance with applicable local requirements.

Any necessary follow-up reports should be completed by updating the original AE eCRF in a timely manner. All follow-up reports should give full details of the event, including an updated assessment of the relationship to the procedure and/or device. When contacting the sponsor regarding SAEs/UADEs, site personnel should be prepared to provide as much information as is available at the time.

Detailed sponsor contact information including emergency contact details will be provided under a separate cover.

11.6. Pregnancy Reporting

Pregnancy itself is not considered to be an adverse event; however, it is a study deviation if the subject becomes pregnant within 24 months postoperatively. If the subject experiences untoward medical occurrences during pregnancy or at delivery, these should be recorded as an adverse event and reported to the sponsor immediately after becoming aware of the event. Female subjects who become pregnant during the study will be followed until the completion of the study. If available, outcomes will be collected on both mother and child.

11.7. Deaths

All subject deaths must be reported to Medtronic and the IRB/EC/REB as soon as possible (but no later than 3 calendar days), after learning of a subject's death, regardless of whether or not the death is related to the device system and/or procedure. The investigator should also attempt to determine, as conclusively as possible, whether such deaths are related to the device system and/or procedure. If the death is evaluated as device and/or procedure related and unanticipated, the event will be reported as a UADE/USADE by Medtronic or its designee to the appropriate Regulatory Authorities.

Any subject death will be reported on the Adverse Event and Study Exit eCRFs. If limited information is known, the Adverse Event eCRF must be completed with available information as soon as possible. The cause of death will be reported on the Adverse Event and death will be reported on the Study Exit eCRFs.

12. Data Review Committees

Medtronic Controlled Information

12.1. Data Monitoring Committee

Ongoing oversight for this study was provided by an independent DMC (Data Monitoring Committee) until enrollment was stopped. Considering enrolment stop and the changes in study design the decision was made to close the DMC and institute a periodic data review by a steering committee and Medtronic medical advisor to monitor the safety of the investigational treatment. The BRAIVE IDE Clinical Study steering committee is a group of at least 3 scientific or subject matter experts which includes pediatric orthopedic surgeons and neurosurgeons and physicians involved in juvenile and adolescent scoliosis. A chairperson from among those members will be identified and the steering committee will operate according to a charter. A review of the FDA annual report and event rate of the study will be made at least annually by steering committee, active investigators and Medtronic medical advisor.

12.2. CRO / Core labs

The information below maybe subject to change during the course of the study. Periodic updates to study contact information will be sent to study sites as need.

Table 11. CRO and Core Laboratory Information

Contact Information	Role
Medical Metrics, Inc [name] USA	Radiographic analysis lab & Image Transfer of intraoperative images Used for eligibility assessment of currently enrolled subjects

13. Statistical Design and Methods

The initial plan was to conduct the primary analysis when all subjects have reached the 2-year visit and an updated analysis when all subjects have reached skeletal maturity. Due to the decision to stop study enrollment, a final analysis will be conducted when all subjects have reached skeletal maturity. An interim analysis may be conducted when all subjects reach 24-month visit in addition to the progressive report requested by FDA. .

13.1. Analysis of Baseline Data

Baseline and pre-operative data will include but are not limited to height, weight, age, and preoperative clinical and radiographic measurements. Demographics and other pre-treatment characteristics will be summarized and characterized with appropriate descriptive statistics. Categorical variables will be

Medtronic Controlled Information

summarized using frequency and percentage. Continuous variables will be summarized using mean, median standard deviation, minimum, and maximum.

13.2. Sample Size

This initial study was designed to show that the investigational device can be used to obtain a statistically significant improvement (>0) in the main thoracic Cobb angle. The initial sample size required to demonstrate a statistically significant improvement of Cobb angle at 24 months as compared to that in the preoperative visit is 24. Medtronic planned to treat 25 subjects. Due to the decision to stop enrollment early, the sample size is 10 at the time of enrollment stop.

13.3. Primary Analysis Population

The primary analysis population will include all subjects who are enrolled and undergo the Braive™ GMS surgical procedure. The primary dataset will be used for all the analyses. For subjects who are treatment failures, the last postoperative observation before the first treatment failure will be carried forward for all additional secondary endpoints and neurological status. No imputation for missing data will be made for other subjects.

13.4. Analyses for Additional Secondary Endpoints

All additional secondary endpoints are listed in the section 5.2.3. For the additional secondary endpoints related to the change from the baseline (pre-op or post-op baseline for instrumented Cobb angle), when the distribution of data is approximately normally distributed, the changes from baseline will be tested using a paired-sample t-test. When the distribution of the data is severely non-normal, a Wilcoxon signed-rank test may be used in place of the paired t-test. In addition, the descriptive statistics including but not limited to mean, standard deviation, median, minimum and maximum will be calculated and presented. For “Status of return to full activity within 3 months per SRS-22”, the number and percentage of subjects returned to full activity within 3 months will be calculated and presented.

Additional analysis will be performed by comparing the postoperative measurements at follow up visits with the measurements at immediate post-op.

13.5. Missing Data Considerations

All analyses will be conducted based on the observed data with no missing data imputation.

13.6. Safety Analysis

13.6.1. Primary Safety Endpoint

The primary safety endpoint is device-related adverse events up to 24-month visit postoperatively.

The number of events, the number and percentage of subjects experiencing device related AE up to 24 months postoperatively will be presented.

In addition, all device-related adverse events up to skeletal maturity (Risser 5) will be summarized.

13.6.2. Secondary Safety Endpoint

The secondary safety endpoints include:

- Procedure-related adverse events up to 24 months
- Secondary spinal surgeries related to the original study device up to 24 months.
- Device deficiency up to 24 months

In addition, all procedure-related and device related adverse events up to skeletal maturity, all secondary surgeries related to the original study device up to skeletal maturity and device deficiency up to skeletal maturity will be summarized.

13.6.3. Adverse events

A listing of all AEs will be provided, and a narrative of each device or procedure related AEs, secondary spinal surgeries, and death will be generated. In addition, summaries of AEs, both overall and by visit, will be provided.

Summaries will be presented for all AEs, SAEs, device or procedure-related AEs and device or procedure-related SAEs. Time course distributions will be provided in addition to cumulative summaries. Time course distributions will be based on the surgery date of the subject and onset dates of AEs, based on continuous time intervals. For overall AE summaries, a subject reporting the outcome at least once during the study period will be included in the frequency count. The percentage of subjects reporting the event at least once during the study period will be reported, and the denominator used in this calculation will be the total number of subjects who are enrolled and who receive the study treatment.

For AE summaries by visit, a subject reporting the outcome at least once during each visit window will be included in the frequency count. The percentage of subjects reporting the outcome at least once during each visit window will be reported, and the denominator used in this calculation will be the number of subjects who have any data reported at that visit (clinical or safety).

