9.1. Schedule of Events

The study schedule, procedures, and methods of assessment are defined in detail to enable compliance with the required activities, and to ensure that the resulting data meet the criteria for evaluability. See Table 6 for visit schedule. The relevant electronic Case Report Forms (eCRFs) along with the applicable source documentation will be completed for each subject. The case report forms are provided separate from this CIP.

Table 6. Schedule of Events

Study Activity	PreOp	Surgery (Day 0)	Discharge	3 Mos.	6 Mos.	12 Mos.	18 Mos.	24 Mos.	Annually ⁴	Unscheduled visit
Visit Window (Days)				±30	±30	±90	±90	±90	±182	
Inclusion/Exclusion Criteria	X									
Informed Consent / Assent	X									
Demographics	X									
Medical History	X									
Physical Assessment	X		X	X	X	X	X	X	X	
PedsQL	X									
SRS-22	X			X	X	X	X	X	X	
Neurological Status	X		X							
Spirometry	X									
Pregnancy Test ¹	X									
Operative Information		X								
Adverse Events and device deficiencies ²	X	X	X	X	X	X	X	X	X	X
Subsequent Spinal Surgical Interventions ²			X	X	X	X	X	X	X	X
Study Deviations	X	X	X	X	X	X	X	X	X	X
Study Exit	X	X	X	X	X	X	X	X	X	X
Radiographic Procedures										
X-Ray P/A Thoracolumbar Spine ³	X		X	X	X	X	X	X	X	X
X-ray Neutral lateral Thoracolumbar Spine ³	X		X	X	X	X	X	X	X	X
X-ray P/A Right Lateral Bending Spine ³	X									
X-ray P/A Left Lateral Bending Spine ³	X									
X-ray P/A Left Hand ³	X									
MRI	X									
StealthStation DICOM ⁵		X								
Intraoperative image ⁶		X								
Risser Score								X ⁷	X ⁷	
Radiographic assessments as per the Radiographic Evaluation Protocol ⁸	X		X ⁹	X	X	X	X	X	X	X

Informed Consent/Assent must be obtained prior to performing any study specific procedure.

¹ A pregnancy test will be administered to all female subjects of child-bearing potential within 72 hours prior to surgery.

² Adverse events, device deficiencies and subsequent spinal surgical interventions are collected at intervals and as reported regardless of follow-up interval.

³ The surgery procedure should occur as soon as possible after the eligibility report has been received from the imaging vendor but no

Medtronic Controlled Information

later than 3 months after the date of acquiring the X-ray images.

⁴ After 24 months, subjects will be followed until skeletal maturity is reached (defined as Risser 5 as assessed by the investigator).

⁵ StealthStation DICOM collection is only applicable to study sites using image guidance.

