9.1.4. Discharge Assessment

The following information will be collected at the discharge assessment (at the time of hospital discharge):

- Physical Assessment (weight and height)
- Imaging (P/A and lateral X-rays)
- Radiographic assessments as per standard of care
- Neurological Status
- Adverse events and/or device deficiencies
- Study Deviations

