9.7. Recording Data

The investigator must ensure that the data reported in the eCRF and all other required study reports are accurate, complete and reported in a timely manner. Data reported on the eCRFs must be consistent with the source documents, and discrepancies between the eCRF and source documents need to be justified in writing, signed and dated by the investigator, and filed in the subject's medical file or appropriate location.

Subject neurological status and instrument accountability can be recorded directly on the eCRF and is considered source data. All other data entered in the eCRFs should be documented in the subject's medical records/source document (electronic or paper), (e.g., hospital records, surgery reports, x-rays, MRIs, CTs, or any other material that contains original information used for data collection including the documentation of AEs and study source document completed by the investigator or site staff). Subject/parent(s)/legal guardian completed questionnaires as well as data collected during subject/parent(s)/legal guardian phone calls will be considered as source data.

This study will be conducted using a Remote Data Capture (RDC) system. The RDC system allows the study centers to enter study data into the sponsor's database over a secure internet connection. Required data will be taken from source documents and directly entered into the study database by authorized site personnel in accordance with applicable regulations.

Every attempt should be made to complete the required onsite clinic visit. However, if the subject is unable to return to the investigational site for their scheduled follow-up visit, the study site can contact the subject and collect the following data remotely using the source document worksheet:

- SRS-22 – phone version or web-based application
- Adverse events and/or device deficiencies

The Principal Investigator or an individual delegated by the Principal Investigator on the Delegation of Authority Log is responsible for documenting and entering data for the study on the eCRFs. Only authorized site study staff can complete eCRFs. eCRFs shall be signed by the Principal Investigator or Sub-investigators (physicians only) as specified on the Delegation of Authority Log included in the Investigator Site File. The Principal Investigator or delegated Sub-Investigator is required to approve all data on eCRFs via electronic signature.

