7.10.3 Adverse Events and Device Deficiencies

A listing of all AEs, SAEs, device or procedure related AEs and SAEs and device deficiencies, secondary spinal surgeries and death will be generated. In addition, summaries of AEs, both overall and by visit, will be provided.

Summaries will be presented for all AEs, SAEs, device or procedure-related AEs, device or procedure-related SAEs and device deficiencies. Time course distributions will be provided in addition to cumulative summaries. Time course distributions will be based on the surgery date of the subject and onset dates of AEs, resulting in continuous time intervals. For overall summaries, a subject reporting the outcome at least once during the study period will be included in the frequency count. The percentage of subjects reporting the event at least once at up to 12-month visit, 24-month visit and skeletal maturity will be reported, and the denominator used in this calculation will be the total number of subjects who are enrolled and who receive the study treatment.

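### The by-visit adverse event summary relies on visit windows that do not join up and on a denominator that partly depends on the outcome

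*Protocol*

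**What the plan says.** Protocol section 13.6.3 plans AE summaries overall, by visit and as time-course distributions. The time-course tables use onset dates on continuous intervals counted from surgery. The by-visit tables follow a different rule. For the numerator, "a subject reporting the outcome at least once during each visit window will be included in the frequency count". The denominator is "the number of subjects who have any data reported at that visit (clinical or safety".

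Neither document defines analysis windows. The only visit windows are the scheduling windows in protocol Table 6 (section 9.1): 30 days either side at 3 and 6 months, 90 days either side at 12, 18 and 24 months, and 182 days either side at annual visits. The Surgery, Discharge and Unscheduled visit columns are AE collection points without a window. A footnote to the same table says that AEs "are collected at intervals and as reported regardless of follow-up interval".

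SAP section 7.10.3 says that "summaries of AEs, both overall and by visit, will be provided", but gives no by-visit numerator or denominator. The percentages it does define are cumulative (to 12 months, 24 months and skeletal maturity) over all treated subjects.

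**The concern.** A table tied to visit windows can place every event only if the windows meet end to end. These do not, while AEs arrive continuously. The denominator raises a second difficulty: whether a subject who missed the visit is counted can depend on whether that subject had an AE to report.

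The protocol's primary objective (section 5.1.1) is now to summarize the safety data, and ten subjects were treated (section 9.1.1). One subject omitted from a row moves its percentage by about 10 points. The by-visit rows could also show a different pattern over time from the time-course table that the same section requires.

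**Working it through.** The plan gives no figure for this table, so there is none to reproduce.

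**Inputs from the documents.** Window half-widths from Table 6; ten treated subjects.

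**Assumptions.** A month is 30.4375 days, with 30 days as a check. The first annual visit is at 36 months. Discharge falls between day 3 and day 10. The absentee and event counts in step 4 are illustrative.

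**Step 1: gaps.** Window = months × 30.4375, rounded, ± half-width.

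| Visit | Target day | Window | Uncovered days before it |
|---|---|---|---|
| 3 months | 91 | 61-121 | 1-60 (60 days) |
| 6 months | 183 | 153-213 | 122-152 (31) |
| 12 months | 365 | 275-455 | 214-274 (61) |
| 18 months | 548 | 458-638 | 456-457 (2) |
| 24 months | 730 | 640-820 | 639 (1) |
| 36 months | 1096 | 914-1278 | 821-913 (93) |

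Up to the close of the 24-month window, 60 + 31 + 61 + 2 + 1 = 155 of 820 days (19%) lie in no numbered window. Later annual windows join up.

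**Step 2: sensitivity.** With 30-day months the main gaps are days 1-59, 121-149 and 211-269 (59 + 29 + 59 = 147 days), and then 811-897. The short gaps near days 456 and 639 vanish. Instead, neighboring windows overlap by one day at days 450 and 630, and by five days between later annual visits, so one report could count in two rows. If the Surgery and Discharge columns absorb events up to discharge on day 3 to day 10, the early gap shrinks to between days 4-60 and days 11-60. The 155 days then become 152 to 145.

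**Step 3: which events are exposed.** The rule turns on reporting. Protocol section 11.2 makes pain, neurological or function symptoms that lead to an unscheduled visit reportable AEs, and that column has no window. Table 10 requires serious events to reach the sponsor within 3 calendar days of the investigator learning of them. Reports will therefore fall between windows. An event reported only there enters no row.

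**Step 4: denominator.** Let *e* attendees have an AE, let *b* absentees have an AE reported, and let *a* absentees have no data. The rule gives (*e* + *b*)/(10 − *a*); over all treated subjects the figure is (*e* + *b*)/10. With *e* = *b* = 1:

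| *a* | By-visit rule | All treated |
|---|---|---|
| 0 | 2/10 = 20% | 20% |
| 1 | 2/9 = 22% | 20% |
| 2 | 2/8 = 25% | 20% |
| 3 | 2/7 = 29% | 20% |
| 4 | 2/6 = 33% | 20% |

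**Step 5: the opposing effect.** Suppose instead that one of two affected subjects reports only between windows. With data from all ten, the row shows 1/10 = 10%, not 20%. With one other subject lacking data, it shows 1/9 = 11%. The two faults pull in opposite directions.

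**The case against.** The strongest reply is that the rule speaks of reporting, whereas section 13.6.3 uses onset dates only for the time-course table. A reader might infer that every event with onset in a gap is lost. The text does not say so: an event that begins on day 40 and is first reported at a 3-month visit held in its window counts in that row. This objection stands, and it limits the point to events reported only between windows.

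A reader might also infer that all of days 1-60 are lost, or that most procedure-related events occur then. Neither is supported. Surgery and Discharge are AE collection points, so in-hospital events can be tabulated there, and the documents give no distribution of events over time. For the same reason the 19% is a share of days, not of events. The clear early gap runs from after discharge to about day 60.

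On the denominator, protocol section 9.7 says that "if the subject is unable to return to the investigational site for their scheduled follow-up visit, the study site can contact the subject", and AE data can be collected that way. An absentee free of AEs may thus enter the denominator; only one with no data at all is left out. The 2/10 comparator also treats that unobserved subject as event-free, so it is a reference and not the true rate.

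Nor should by-visit counts be expected to add up to the cumulative count. A subject with events in two windows appears twice by visit and once overall, and contiguous intervals would not change that.

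Two defenses do not succeed. The term visit window might be meant as contiguous analysis windows, but neither document defines any. SAP section 7.1.1 keeps out-of-window visits in the analysis, but does not say in which row an AE reported at such a visit belongs.

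**Conclusion.** The point holds at minor severity. Followed literally, the rule omits events reported only between Table 6 windows and uses a denominator that partly depends on the outcome. The gaps at days 122-152, 214-274 and 821-913 shift by only a few days, up to about 16, with the month conversion. The early gap also depends on the day of discharge, and the one- and two-day gaps on the conversion alone. The denominator effect needs at least one subject without any data at the visit; for one to four such subjects the inflation relative to all treated subjects is 10/(10 − *a*), or 1.11 to 1.67.

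A reader might conclude that the by-visit percentages are always too high. The documents do not support that, because the gaps act the other way. No separate rate for absentees is planned, so none is misstated. Nor is the primary safety result at risk. The listing of all AEs, the overall summaries, the continuous time-course tables and the 24-month primary and secondary safety endpoints do not use this rule. Beyond this one descriptive table, the fault reaches only the summaries of subsequent spinal surgeries, and only if those are made by visit. Protocol section 13.6.5 and SAP section 7.10.4 say that they will follow the AE approach.

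**What to change.** In protocol section 13.6.3, and identically in SAP section 7.10.3, replace the by-visit rule as follows:

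- Assign each AE by onset date to contiguous, non-overlapping intervals: surgery to discharge, discharge to the 3-month point, 3 to 6 months, and so on to skeletal maturity. State the conversion of months to days once.
- Count each subject at most once per interval.
- Use as denominator the subjects still under follow-up at the start of the interval, whether or not they attended or reported anything.
- State whether surgery summaries are made by interval and, if so, apply the same rule.

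Alternatively, delete the by-visit table and keep the time-course table with that denominator. Either choice costs a wording change in both documents and slight reprogramming. No additional data are needed, because AE onset dates and surgery dates are already required for the time-course tables.
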